## 5. Research Design and Technical Route

### 5.1 General Research Design

this study was a single @-@ center, observational study of patients with type 2 diabetes mellitus and chronic kidney disease, aged 18 to 56 years.

sex, prospective cohort study.

### 5.2 Technical Roadmap

Note: DKD: Diabetic Kidney Disease; CGM: Continuous Glucose Monitoring; TIR: Time in Range; GV: Glucose Variability.

### 5.3 Study Site and Study Population

**5.3.1 Study site:** From July 1, 2025 to December 31, 2025, the subjects were recruited in the inpatient department of endocrinology department of the Eighth Affiliated Hospital of Sun Yat-sen University according to the inclusion and exclusion criteria.

**5.3.2 Study population:** patients with type 2 diabetes and chronic kidney disease (DKD) (n=270)

#### 1) Inclusion Criteria:

- ① Age 18-65 years;
- ② The diagnosis of DKD meets the relevant criteria in the "China Diabetes Nephropathy Prevention and Treatment Guidelines (2021 Edition)";
- ③ Type 2 diabetes mellitus, treated with insulin analogues or oral antidiabetic drugs, diagnosed according to the 1999 WHO criteria;
- ④ no changes in the antidiabetic regimen were made for at least 3 months before enrollment.
- ⑤ informed consent was obtained voluntarily.

## **2) Exclusion criteria:**

- ① The patients with diabetes mellitus complicated with ketoacidosis, primary glomerulonephritis, nephrotic syndrome, lupus nephritis and other primary or secondary kidney diseases.
- ② The body was in a state of stress such as infection and trauma.
- ③ women who are pregnant, breastfeeding, or planning to become pregnant next month;
- ④ severe skin lesions, such as extensive eczema, extensive scarring, extensive tattoos, papular dermatitis, severe edema and psoriasis;
- ⑤ Sensory surface of the sensor is scarred due to severe skin burns, scalds, sunburns, trauma, ulcers, surgery, etc.
- ⑥ coagulation dysfunction, anemia or abnormal hematocrit;
- ⑦ Patients with chronic gastrointestinal diseases or a history of biliary or gastrointestinal surgery were excluded from the study.
- ⑧ consumed probiotics, prebiotics, or received antibiotic treatment for more than 3 days in the past 3 months; consumed yogurt or yogurt-containing foods or beverages in the past week.

## **3) Exit criteria:**

researcher decided withdrawal

- ① those who had adverse reactions or serious adverse events or other complications and special physiological changes, and who should be stopped from the study and taken emergency treatment measures such as medication, hospitalization or surgery according to the judgment of the investigator;
- ② Women became pregnant during the study;
- ③ Serious violation of the study protocol, such as enrollment in the study despite not meeting the inclusion criteria. Participants may withdraw voluntarily.
- ① provisional withdrawal of informed consent;
- ② Participants cannot tolerate certain tests;

③ unforeseen events occurred during the study that made it impossible for the participant to continue the study.

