### (3) Follow-up in the Queue:

- 1) follow-up time: 3 years after discharge.
- 2) Follow-up methods: outpatient follow-up, telephone follow-up and review of relevant medical records.
- 3) Outcome measures:

**① Primary end point:** progression of DKD. Progression of DKD was defined as renal failure (requiring transplantation or dialysis, or persistent eGFR <15 ml/min/1.73 m^2) or a persistent decline of 30% in eGFR from baseline.

**② Secondary End Points:** I. Cardiogenic Death: Death caused by cardiac disease or related complications. II. Major Adverse Cardiovascular Events (MACE): Including major cardiovascular events such as myocardial infarction, stroke, and unstable angina. III. Kidney Transplantation: Successful cases of kidney transplantation surgery. IV. Hypoglycemic Events: Record the frequency and severity of hypoglycemia occurrences.

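### Exit criterion ① lets the investigator remove patients after serious events, without exempting endpoint events or keeping those patients in outcome follow-up

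*Protocol*

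**What the plan says.** Protocol section 5.3.2, Exit criteria, lists withdrawals decided by the researcher. The first concerns "those who had adverse reactions or serious adverse events or other complications and special physiological changes", and continues: "who should be stopped from the study and taken emergency treatment measures such as medication, hospitalization or surgery according to the judgment of the investigator". It names no period and no exception, and does not say whether a patient who exits is still followed for outcomes.

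The endpoints in sections 3.1 (3) and 5.5 (3) include events of the same kind:

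- Primary endpoint, DKD progression: "renal failure (requiring transplantation or dialysis, or persistent eGFR <15 ml/min/1.73 m 2 ) or a persistent decline of 30% in eGFR from baseline".
- MACE: "Including major cardiovascular events such as myocardial infarction, stroke, and unstable angina".
- "Kidney Transplantation: Successful cases of kidney transplantation surgery".
- "Hypoglycemic Events: Record the frequency and severity of hypoglycemia occurrences".

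Section 5.5 (3) sets three years of follow-up after discharge by clinic visit, telephone and record review. Section 5.6 ticks DKD progression and MACE at Visits 4 to 6, deaths at Visits 1 to 6, and adverse event monitoring at Visits 1 to 3 only. Section 5.8.2 names Cox regression for time-to-event data.

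**The concern.** A myocardial infarction, a stroke, severe hypoglycemia or the start of dialysis is a serious event or complication treated with drugs, admission or surgery. Each therefore fits the description in the exit rule, and each is also something the cohort exists to observe. If the investigator applies the rule after such an event, the protocol offers nothing that keeps the patient under observation.

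Cox regression assumes that a censored patient has the same future risk as comparable patients still in follow-up. A patient removed because of a serious event need not meet that assumption. If risk is higher after the event, progression and death after it go unrecorded and their frequency is understated. Because exit is a matter of judgment without stated criteria, the loss may also differ between investigators. Outcomes that were never collected cannot be recovered at analysis.

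**Working it through.** **Step 1. What exit can lose, event by event.**

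| Event that prompts exit | Already counted as | What may be lost afterwards |
|---|---|---|
| Dialysis, transplantation, persistent eGFR <15 | Primary endpoint | No first primary event; later MACE or cardiac death |
| Non-fatal infarction, stroke, unstable angina | First MACE | DKD progression, cardiac death |
| Severe hypoglycemia | Hypoglycemic event | DKD progression, MACE, cardiac death |
| Other serious event or complication | Nothing | All later endpoints |
| Any of these during a falling eGFR | As above | A 30% decline not yet confirmed as persistent |

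For the primary endpoint, the loss is confined to patients who exit before progression is established.

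**Step 2. Does the wording limit the rule to the CGM fortnight?** The exit criteria contain no such limit. Two neighbouring criteria, pregnancy and unforeseen events, refer to the course of the study, not to 14 days. Only the adverse event row in section 5.6 points to a shorter window.

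**Step 3. Reproduce the plan's sample size (section 5.4).** Inputs: 156 progression events in 975 patients, at least 30 events required, 10% allowance for loss.

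- Event proportion: 156/975 = 0.16.
- Patients needed: 30/0.16 = 187.5, as stated.
- With the allowance: 187.5 × 1.10 = 206.25, or 187.5/0.90 = 208.3. Both are consistent with the planned 210.

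**Step 4. How much room is there?**

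- Expected events with no loss: 210 × 0.16 = 33.6.
- After the planned 10% loss, if unrelated to outcome: 33.6 × 0.90 = 30.2.
- Let q be the share of would-be progressors who exit before progression is recorded. Recorded events = 33.6 × (1 − q). This falls below 30 when q > 1 − 30/33.6 = 10.7%.

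The documents give no value for q, so the following are assumptions that show the range:

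| q (assumed) | Events recorded |
|---|---|
| 10% | 30.2 |
| 20% | 26.9 |
| 30% | 23.5 |

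**Step 5. Same total loss, but related to outcome.** Keep the planned loss of 21 patients (10% of 210) and let it be k times as likely in progressors. Loss probability in non-progressors is 0.10/(0.84 + 0.16k), and in progressors k times that.

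| k (assumed) | Loss in progressors | Events recorded |
|---|---|---|
| 1 | 10.0% | 30.2 |
| 2 | 17.2% | 27.8 |
| 3 | 22.7% | 26.0 |

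The allowance therefore meets the stated minimum only if loss is essentially unrelated to outcome.

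**Caveat on the base.** The 16% was observed over a mean of 4.7 years, while this study follows patients for three. At a constant hazard (an assumption), the three-year proportion is 1 − (1 − 0.16)^(3/4.7) = 10.5%, or about 22 events in 210, already below 30 before any exit. That is a separate matter. The 10.7% threshold holds only on the plan's own figures.

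**The case against.** **Exit is discretionary.** A reader might infer that every patient with a MACE or other serious event is dropped. The text does not support that: the investigator must also judge that the patient should stop. This stands, and it means the number who would exit cannot be known from the documents. It does not remove the problem, since discretion exercised after a serious event is still related to outcome.

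**The rule may be meant for the CGM phase.** Adverse event monitoring is scheduled only at Visits 1 to 3, progression and MACE have their own later rows, and most risks named in section 2.2.2 are procedural: skin irritation, bruising and infection. This is a plausible reading. But the exit criteria do not state it, and hypoglycemic events, which are an endpoint, have no row of their own. A patient stopped during the fortnight would also still lose the three-year follow-up.

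**There is something to stop.** One might say that an observational cohort has nothing to withdraw, so exit can only mean the end of observation. That goes too far: section 5.5 (2) includes CGM wear, dietary guidance and glucose-lowering regimens. The gap is that the protocol does not distinguish stopping these from leaving follow-up.

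**Triggering endpoint events are counted.** This also stands. Dialysis or transplantation is itself the primary event, which narrows the loss to later outcomes and unconfirmed eGFR decline.

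**Handling of exits belongs in the SAP.** How exits enter the analysis may be settled there, and the SAP is not shown. The point here concerns data collection, which the protocol fixes.

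**Conclusion.** The concern holds as an unresolved conflict between the exit rule and the follow-up plan, with moderate confidence. As written, the protocol permits follow-up to end because of a serious event, including one of the study's own endpoints, and nothing in it keeps those patients under observation. Where the rule is applied, censoring is related to outcome.

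The size is unknown, because no exit rate is given. What can be said on section 5.4's own figures is that the margin is thin: 33.6 expected events against 30, so that losing more than about 11% of progressors breaks the minimum.

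Two stronger readings are not supported. A definite number of lost events cannot be given, since it would need assumed event rates, assumed risk after the event and an assumed frequency of exit. Nor can it be said that the loss falls mainly on patients with high glycemic variability, because that association is what the study sets out to test.

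**What to change.** Reconcile exit criterion ① with sections 5.5 (3) and 5.6 by adding one sentence, for example: an adverse event or endpoint event may lead the investigator to end CGM wear or other study procedures, but it does not end outcome follow-up, which continues by the planned visits, telephone contacts and record review to three years unless the participant withdraws consent. If the rule is intended for the CGM phase only, say that as well.

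This leaves the investigator's judgment intact and changes no treatment rule. It uses contacts already planned for every patient. The cost is a short protocol amendment, which needs ethics committee approval under section 6.1.

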## 5.4 Methods for Determining the Required Sample Size for Research

This exploratory study investigates the impact of gut microbiota and related metabolites on prognosis in diabetic kidney disease (DKD) patients. To achieve this, patients will be divided into two groups based on adverse prognosis outcomes, with subsequent comparisons of gut microbiota and metabolite differences between groups. To minimize microbial variations caused by individual differences, each group requires at least 30 participants, meaning there must be at least 30 patients with adverse prognosis events. Drawing from existing research, a 2023 study published in *\*Diabetes Care\** [Diabetes Care.2023;46(4):868-873.] included 975 DKD patients with an average follow-up of 4.7 years, reporting 156 major outcomes of DKD progression. Consequently, the total sample size was calculated as  $975/156*30=187.5$ . Considering potential dropouts and incomplete responses, we typically increase the sample size by 10%, ultimately enrolling 210 patients as the modeling cohort. Additionally, 60 DKD patients were included as a validation cohort. During actual recruitment, sample size adjustments may be made based on factors such as recruitment speed and data quality. Regular assessments of sample adequacy should also be conducted to ensure statistical power.

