**(3) Study endpoint:**

**① Primary end point:** progression of DKD. Progression of DKD was defined as renal failure (requiring transplantation or dialysis, or persistent eGFR <15 ml/min/1.73 m^2) or a persistent decline of 30% in eGFR from baseline.

**② Secondary End Points:** I. Cardiogenic Death: Death caused by cardiac disease or related complications. II. Major Adverse Cardiovascular Events (MACE): Including myocardial infarction, stroke, unstable angina pectoris, and other significant cardiovascular events. III. Kidney Transplantation: Successful cases of kidney transplantation surgery. IV. Hypoglycemic Events: Documentation of the frequency and severity of hypoglycemia occurrences.

**(4) Specific objectives:** I. Evaluate the relationship between GV and prognosis in patients with DKD and determine the optimal GV control target. II. Screen for biomarkers of gut microbiota, metabolites, and inflammatory factors associated with DKD prognosis.

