#### **(4) 16S RNA Sequencing Analysis and Non-Target Metabolic Analysis**

We performed 16S rRNA sequencing, non-target metabolic analysis, and inflammatory factor detection on collected fecal and blood samples to compare differences in gut microbiota, metabolites, and inflammatory factors across different prognostic groups, and to identify prognostic markers. We also compared the differences in gut microbiota, metabolites, and inflammatory factors among patients with high glycemic variability, intermediate glycemic variability, and low glycemic variability. Furthermore, we identified gut microbiota markers and serum metabolic markers associated with high glycemic variability.

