### 5.8.2 Statistical Analysis

Descriptive statistical analysis was performed on the collected data. Continuous variables were presented as mean  $\pm$  standard deviation (or median and interquartile range), while categorical variables were expressed as frequency and percentage. For intergroup comparisons of continuous variables, independent samples t-test or Mann-Whitney U-test was selected based on data normality. In cases involving multiple group comparisons, one-way ANOVA or Kruskal-Wallis test was employed. Categorical variable comparisons utilized chi-square test or Fisher's exact test to assess significant differences between groups. To evaluate relationships among multiple variables, linear regression was applied to continuous variables, logistic regression to categorical variables, and Cox proportional hazards regression to time-to-event data. These analyses adjusted for potential confounders such as age, sex, disease duration, and baseline glucose levels to ensure result accuracy and reliability. Confounding factors were included in regression analyses to minimize their impact. Additionally, propensity score matching was used to balance baseline characteristics between groups, ensuring comparability and enhancing the internal validity of the study results.

After adjusting for various covariates, we examined the association between adverse prognosis, hyperglycemic variability, and the gut microbiota  $\alpha$ -diversity index. The relationship between hyperglycemic variability, adverse prognosis, and  $\beta$ -diversity differences was tested using genus-level Bray-Curtis distance-based permutation ANOVA (PERMANOVA). Using MaAsLin, we identified gut microbiota communities potentially associated with adverse prognosis and hyperglycemic variability by comparing hyperglycemic variability groups with hypoglycemic variability groups, and prognostic favorable groups with unfavorable groups. OPLS-DA was employed to identify target metabolites potentially related to hyperglycemic variability and adverse prognosis, with adjustments made through linear regression. Mediation analysis was conducted to evaluate whether gut microbiota metabolism might mediate the association between hyperglycemic variability and adverse prognosis. Sensitivity analysis was performed to test the robustness of the mediation effect.

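### Screening prognostic markers only by favorable versus unfavorable outcome group discards more than half of the information in eGFR change; a continuous eGFR screen alongside it is a cheap improvement

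*Protocol*

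**What the plan says.** Three places in the protocol describe the marker screen as a contrast between outcome groups.

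- Section 5.4, which sets the sample size: "patients will be divided into two groups based on adverse prognosis outcomes, with subsequent comparisons of gut microbiota and metabolite differences between groups". It then asks that "each group requires at least 30 participants, meaning there must be at least 30 patients with adverse prognosis events".
- Section 5.5(4): the laboratory data are used to "compare differences in gut microbiota, metabolites, and inflammatory factors across different prognostic groups".
- Section 5.8.2, for the MaAsLin analysis: features are found "by comparing hyperglycemic variability groups with hypoglycemic variability groups, and prognostic favorable groups with unfavorable groups".

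The primary endpoint in section 3.1(3), repeated in section 5.5(3), is renal failure or "a persistent decline of 30% in eGFR from baseline". Section 5.8.2 also lists linear regression for continuous variables and Cox regression for time-to-event data, with adjustment for confounders, but links neither to the marker screen. No section names eGFR slope or eGFR change as an outcome. In the visit table of section 5.6, renal function is ticked at Visit 2 only; Visits 4 to 6 carry progression events, MACE and death, but no renal function test.

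**The concern.** Whether a patient has lost 30% of eGFR cannot be determined without follow-up eGFR. Once those values exist, the two-group screen reduces each patient to yes or no. A persistent 29% loss counts with the stable patients, a 30% loss counts with those on dialysis, and all variation within the larger group is ignored.

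Specific objective II in section 3.1 is to find markers of prognosis. With 20 to 30 patients in the smaller group, a modest marker of renal decline may well be missed, and one that does reach significance is likely to be overestimated. A continuous outcome would draw on every patient, so the question is how much the split costs.

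**Working it through.** **Inputs from the protocol.** Section 5.4 cites a study that "included 975 DKD patients with an average follow-up of 4.7 years, reporting 156 major outcomes of DKD progression", asks for 30 events, adds 10%, and arrives at 210 patients for the modeling cohort. Follow-up is 3 years (section 5.5(3)).

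**The plan's own figure.** 975/156 × 30 = 187.5. Adding 10% gives 187.5 × 1.10 = 206.25, so 207; dividing by 0.90 gives 208.3, so 209. The stated 210 is reproduced up to rounding. The power figures below use n = 188, the number before the allowance for dropout.

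**Event share.** 156/975 = 16.0% over a mean of 4.7 years. Scaled to 3 years under a constant hazard: 1 − (1 − 0.16)^(3/4.7) = 10.5%. Among 210 × 0.90 = 189 completers this gives about 30 events at 16% and about 20 at 10.5%.

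**Assumptions (not in the protocol).** Two-sided alpha is 0.05, or 0.001 to stand for a multiplicity-adjusted screen. The correlation r between marker and eGFR change runs from 0.10 to 0.40. The event is a threshold on a normal, fully observed eGFR change.

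**Information kept by the split.** Relative efficiency = φ(z_p)² / [p(1 − p)], where p is the event share, z_p the normal quantile at p and φ the normal density.

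- p = 0.16: 0.2433² / 0.1344 = 0.44. So 188 patients count as 188 × 0.44 ≈ 83.
- p = 0.105: 0.1822² / 0.0942 = 0.35. So 188 patients count as 188 × 0.35 ≈ 66.

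**Power.** Fisher-z test of a correlation: Φ(atanh(ρ)·√(n − 3) − z_(1−α/2)), plus a negligible opposite tail. For the continuous outcome ρ = r. For the split ρ = r·φ(z_p)/√[p(1 − p)], that is 0.664r at 16% events and 0.593r at 10.5%.

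Worked case, r = 0.20 and 16% events:

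- Continuous: 0.2027 × 13.60 − 1.96 = 0.80, power 78.7%.
- Split: ρ = 0.133, 0.1335 × 13.60 − 1.96 = −0.14, power 44.3%.

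| alpha | r | continuous | split, 16% events | split, 10.5% events |
|---|---|---|---|---|
| 0.05 | 0.10 | 27.6% | 14.8% | 12.7% |
| 0.05 | 0.15 | 53.8% | 27.4% | 22.8% |
| 0.05 | 0.20 | 78.7% | 44.3% | 36.8% |
| 0.05 | 0.25 | 93.5% | 62.5% | 52.9% |
| 0.05 | 0.30 | 98.8% | 78.4% | 68.7% |
| 0.05 | 0.40 | 100% | 95.9% | 90.8% |
| 0.001 | 0.20 | 29.7% | 7.0% | 4.8% |
| 0.001 | 0.30 | 82.1% | 29.3% | 19.9% |
| 0.001 | 0.40 | 99.3% | 65.9% | 50.0% |

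A simulation of the same model (4,000 runs per setting) agreed to within about 2 percentage points.

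**Sensitivity to the idealised event.** These runs simulate eGFR courses for n = 210 with assumed inputs.

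- *Noisy yearly eGFR, decline confirmed at two visits* (mean slope −3 to −3.5 and slope SD 4 mL/min/1.73 m² per year, within-patient SD 5 to 8, 19 to 26 events): at r = 0.20, power was 20–21% split against 57–72% for the slope; at r = 0.40, 60–67% against above 99%.
- *About 15 events, 40% of yearly eGFR values missing:* slope power at r = 0.20 fell from 72% to 49%.
- *About 15 events, marker flagging only a subgroup of rapid progressors:* the split kept 57–62% of the slope's power.

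The direction was the same throughout; the size was not.

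**The case against.** The strongest reply is that a clinical event endpoint is legitimate, that the study calls itself exploratory, and that a supplementary outcome can be left to a statistical analysis plan. The adverse outcomes also go beyond eGFR: section 3.1(3) lists cardiac death and MACE, and section 3.2.1 makes all-cause death the endpoint of the prediction model. An eGFR slope cannot screen for those, and it is cut short by dialysis, transplantation or death. All of this stands, and it limits the remedy to an addition. It does not remove the point, because the protocol itself fixes the two-group contrast and sizes the study on it.

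A reader might infer four stronger things that the documents do not support.

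- *That power is more than halved in most cases.* Information is more than halved; power is a different quantity. At two-sided 0.05 and 16% events the split keeps 0.51 to 0.56 of the continuous power for r = 0.10 to 0.20, 0.79 at r = 0.30 and 0.96 at r = 0.40. More than halving across most of the range needs a stricter alpha, or an event tied less closely to slope; the protocol states no alpha, power or effect size.
- *That 210 to 270 eGFR trajectories will lie unused.* Section 5.6 does not schedule renal function after Visit 2, and section 5.5(3) allows telephone follow-up and record review. The series has to be added.
- *That the 30-to-180 imbalance measures the loss.* The balanced equivalent, 4 × 30 × 180/210 = 103, reflects unequal group sizes. A 105/105 split would score the full 210 and still dichotomise eGFR.
- *That no other outcome model is planned.* Cox and linear regression are named in section 5.8.2; they are just not tied to the screen.

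**Conclusion.** The point holds as a cheap improvement to the plan; the two-group comparison is not itself an error. For DKD progression, that comparison keeps about 44% of the information in eGFR change at 16% events and about 35% at 10.5%, given a threshold on a normal, fully observed eGFR change.

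The effect on power is less certain, because it rests on marker strength, alpha, event count and eGFR completeness, none of which the protocol gives. It is substantial for modest markers, small for strong ones at 0.05, and larger with fewer events or a multiplicity-adjusted alpha. Renal failure events, the persistence requirement and noisy or missing yearly eGFR make the real gain uncertain. The evidence does not support replacing the event-based screen with eGFR slope.

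**What to change.** 1. In section 5.8.2, add rate of eGFR change as a pre-specified continuous screening outcome for DKD progression. Use a linear mixed model with a marker-by-time interaction, all patients, and the covariates already listed there. State that it stands alongside the two-group comparison and not in its place.
2. In the same section, tie the Cox model already planned to the marker screen for progression, MACE and death.
3. In the visit table of section 5.6, tick renal function (eGFR) at Visits 4 to 6. The primary endpoint requires this in any case.
4. Specify a sensitivity analysis for eGFR series cut short by dialysis, transplantation or death.

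**Cost:** one extra model, its sensitivity analysis, and the collection and recording of yearly eGFR. No extra patients are needed and the primary endpoint is unchanged. The downside is that slope is a surrogate and can reflect short-term treatment effects on eGFR, which is why the event analysis stays.

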## **3.2 Secondary Purpose**

### 3.2.1 Construct a Predictive Model to Predict the Risk of Adverse Prognosis in Patients With DKD.

- (1) **Study subjects:** patients with diabetic nephropathy.
- (2) **Exposure factors:** glycemic variability index, clinical indicators, intestinal flora, serum metabolites, inflammatory factors.
- (3) **study OUTCOMES:**
  - (1) **Primary end point:** death from any cause, including death from all causes.
  - (2) **Secondary end point:** Unintentional major cardiovascular events (MACE): major cardiovascular events including myocardial infarction, stroke, and unstable angina pectoris.
- (4) **Specific objectives:** Construct a prediction model by incorporating the above indicators to predict the prognosis of DKD patients.

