#### **5.6 Experimental Scheme**

Step	Period	Filter period	Period of wearing CGM			Follow-up period		
	Study follow-up	Visit 0	Visit 1	Visit 2	Visit 3	Visit 4	Visit 5	Visit 6
	Study date (days)	1 day before enrollment	1 day after enrollment	7 days after enrollment	14 days after enrollment	Within 1 year after enrollment	Within 2 years after enrollment	Within 3 years after enrollment

1	Selection and exclusion criteria	✓						
2	Sign the informed consent form.	✓						
3	Adorn CGM		✓					
4 clinical data	Basic information of the subjects		✓					
	Clinical diagnosis		✓					
	Personal history		✓					
	History of past illness		✓					
	Check-up		✓					
5 clinical examination Inspection	Routine blood test			✓				
	Liver function			✓				
	Renal function			✓				
	HbA1c			✓				
	Blood fat			✓				
	Fasting insulin (FIns)			✓				
	Blood sugar			✓				
	Thyroid function			✓				
	Coagulation function			✓				
6	Medication during CGM monitoring				✓			
7	Fecal collection		✓					
8	Blood collection		✓					
9	Medications taken after discharge				✓			

10	Download the CGM report				✓			
11	Fecal microbiota sequencing					✓		
12	Metabolite assay in serum					✓		
13	Progression events of DKD during follow-up					✓	✓	✓
14	Assessment of MACE events during follow-up					✓	✓	✓
15	Death events during follow-up		✓	✓	✓	✓	✓	✓
16	Adverse event monitoring		✓	✓	✓			
17	Deviation from plan record		✓	✓	✓	✓	✓	✓
18	Fill in CRF		✓	✓	✓	✓	✓	✓

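### 'Adverse prognosis' is sized on DKD progression in 5.4 but means all-cause death and MACE for the model in 3.2.1, and the prognostic groups in 5.5(4) and 5.8.2 are tied to neither

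*Protocol*

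**What the plan says.** Protocol 5.4 sets up the prognosis comparison of microbiota and metabolites: "patients will be divided into two groups based on adverse prognosis outcomes". It adds that "there must be at least 30 patients with adverse prognosis events". It does not name the adverse outcome, but takes the event rate from a published cohort that "included 975 DKD patients with an average follow-up of 4.7 years", "reporting 156 major outcomes of DKD progression". The resulting 210 patients are called the modelling cohort.

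The primary endpoint in 3.1 and again in 5.5(3) is DKD progression: renal failure or a persistent 30% fall in eGFR. Death is not a component. Cardiac death, MACE, kidney transplantation and hypoglycemia are secondary.

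Section 3.2.1, whose heading announces a model for the risk of adverse prognosis, gives its primary endpoint as "death from any cause, including death from all causes" and its secondary endpoint as MACE. Progression is not listed.

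The first hypothesis in 2.1.4 concerns adverse cardiovascular events. Section 5.5(4) compares prognostic groups, and 5.8.2 describes "comparing hyperglycemic variability groups with hypoglycemic variability groups, and prognostic favorable groups with unfavorable groups"; neither names an endpoint for prognosis. The schedule in 5.6 has a row for "Death events during follow-up", ticked from Visit 1 to Visit 6.

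**The concern.** One term carries several outcomes, and the parts of the protocol that use it depend on each other. Section 4.1.2 screens biomarkers for poor prognosis, 4.1.4 builds the prediction model on screened factors, and 5.4 sizes the cohort used for modelling. If screening follows 5.4 and the model follows 3.2.1, markers are selected for their association with renal progression and then asked to predict death or MACE. The sample-size argument would also be carried over to outcomes for which it was never made.

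A second question follows. A two-group split has to place every patient somewhere. With an endpoint that excludes death, someone who dies early with stable eGFR has no adverse event, and no rule keeps that patient out of the favourable group.

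**Working it through.** **1. The outcomes side by side**

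| Protocol section | Outcome attached to prognosis | Role of death |
|---|---|---|
| 2.1.4, first hypothesis | Cardiovascular events | Not stated |
| 3.1 and 5.5(3), primary | DKD progression | Not a component; cardiac death is secondary |
| 3.2.1 | All-cause death (primary), MACE (secondary) | Primary; progression absent |
| 5.4 | Unnamed; rate taken from DKD progression | Not in the rate used |
| 5.5(4), 5.8.2 | Prognostic groups without an endpoint | Not stated |

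**2. The plan's own figure.** Inputs from 5.4: 975 patients, 156 progression outcomes, 30 events required, 10% allowance.
- Event proportion: 156/975 = 0.16.
- Patients for 30 events: 975/156 × 30 = 187.5, as stated.
- With the allowance: 187.5 × 1.10 = 206.25, or 187.5/0.90 = 208.3. Both agree with the stated 210 after rounding.
- Expected progression events at 16%: 210 × 0.16 = 33.6, or 189 × 0.16 = 30.2 among the 189 left after 10% loss.

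The figure reproduces, but only if adverse prognosis means DKD progression.

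**3. The same cohort under the primary endpoint of 3.2.1.** The protocol gives no mortality rate, so 2-6% over 3 years is an assumption.
- Deaths in 210: 210 × 0.02 = 4.2; 210 × 0.06 = 12.6.
- Patients needed for 30 deaths, before dropout: 30/0.02 = 1500; 30/0.06 = 500.

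No MACE rate is given either, so the MACE count cannot be worked out.

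**4. Deaths in the favourable group under the progression reading.** The number of progressors is bracketed by two values.
- Upper: 33.6, the 16% taken unscaled.
- Lower: the 16% scaled from a mean of 4.7 years to 3 years at constant hazard, 1 − 0.84^(3/4.7) = 0.105, and 210 × 0.105 ≈ 22.1.
- Non-progressors: 210 − 33.6 = 176.4, or 210 − 22.1 = 187.9.
- Share who died: 4.2/187.9 = 2.2% to 12.6/176.4 = 7.1%.

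This is an upper bound for the assumed mortality, because it treats every death as occurring without prior progression. If a fraction f of the favourable group consists of deaths whose profile equals that of progressors, the difference in group means shrinks by the factor 1 − f, here by about 2-7%.

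**The case against.** Several counter-arguments have force.

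- Section 3.2.1 sets endpoints for a prediction model; it does not define the omics split. A protocol may have several endpoints, and a patient may be a case for one and a control for another. This stands: the documents do not give two explicit definitions of the same split. The difficulty is that 5.4 sizes the modelling cohort on progression, 3.2.1 omits progression from the model, and the model draws on markers screened for prognosis.
- A reader might infer that every omics comparison is affected. The text does not support this. Sections 3.2.2, 4.1.3, 5.5(4) and 5.8.2 also compare glycemic variability groups, which do not use the prognosis split.
- A reader might infer that the protocol analyses deaths without progression as favourable. No section says so. Section 5.4 speaks of outcomes in the plural, which leaves room for a composite, and exclusion is not ruled out. It is only the default result of a binary split on an endpoint without death.
- A reader might add the deaths to the progressors and report how far the adverse group grows. That composite matches neither 5.4 nor 3.2.1.
- Rules for deaths and competing events often sit in an analysis plan, which is not shown. That covers the technical detail. It does not cover conflicting outcomes within the protocol, which an analysis plan could settle only by overriding one section.

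**Conclusion.** The inconsistency is real and worth correcting before outcomes accrue. It affects the prognosis-based omics comparisons and the prediction model. The firm part needs no assumption: the 30-event requirement and the 210 patients were derived for DKD progression alone, 3.2.1 models other outcomes, and the groups in 5.5(4) and 5.8.2 are unassigned.

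The practical size depends on an assumed 3-year mortality. At 2-6%, a model for death would rest on about 4-13 events in place of 30. The placement of deaths is the smaller matter: at most about 2-7% of the favourable group, with a modest dilution if those patients resemble progressors. A general claim of bias toward the null goes beyond the documents, since nothing shows that patients who die share the progressors' microbiota and metabolite profile.

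**What to change.** - In 5.4, 5.5(4) and 5.8.2, define the unfavourable group as patients with DKD progression, the primary endpoint, within 3 years.
- In 3.2.1, make DKD progression the primary outcome of the model. Keep all-cause death and MACE as separately labelled secondary outcomes, and state that the 30-event basis does not apply to them and that their models are exploratory.
- Align the hypothesis in 2.1.4 with this.
- State that patients who die before progression are not counted as favourable. Report them separately, add a sensitivity analysis that counts them as unfavourable, and treat death as a competing event when absolute progression risk is reported.

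The cost is a few sentences in five sections. No new data are needed, because deaths are already recorded at each visit from Visit 1. The downside is that a few patients leave the two-group comparison (about 4-13 at most on the assumed rates), which conditions it on survival; the sensitivity analysis shows whether that matters.
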